9.5.4.5 Breaking the Blind

As of 14 Jul 2018, the subjects' treatment assignment is no longer blinded.

9.5.4.6 Regulatory Reporting of Adverse Events

Adverse events will be reported by the sponsor or a third party acting on behalf of the sponsor to regulatory authorities in compliance with local and regional law and established guidance. The format of these reports will be dictated by the local and regional requirements.

All studies that are conducted within any European country will comply with European Good Clinical Practice Directive 2005/28/EC and Clinical Trial Directive 2001/20/EC. All SUSARs will be reported, as required, to the competent authorities of all involved European member states.

9.5.5 Completion/Discontinuation of Subjects

A subject may elect to discontinue the study at any time for any reason. All subjects who discontinue the study are to complete the study's early discontinuation procedures indicated in the Schedule of Procedures/Assessments ([Table 6](#)) and Schedule of Assessments After the Data Cutoff for the Primary Analysis ([Table 7](#)).

The investigator will promptly explain to the subject involved that the study will be discontinued for that subject and provide appropriate medical treatment and other necessary

measures for the subject. A subject who has ceased to return for visits will be followed up by mail, phone, or other means to gather information such as the reason for failure to return, the status of treatment compliance, the presence or absence of AEs, and clinical courses of signs and symptoms.

Subjects who discontinue early from the study will be discontinued for 1 of these primary reasons: AE(s), lost to follow-up, subject choice, progression of disease, withdrawal of consent, pregnancy, study terminated by sponsor, or other. In addition to the primary reason, the subject may indicate 1 or more secondary reason(s) for discontinuation. Study disposition information will be collected on the Subject Disposition CRF.

A subject removed from the study for any reason may not be replaced.

9.5.6 Abuse or Diversion of Study Drug

Not applicable.

9.5.7 Confirmation of Medical Care by Another Physician

The investigator will instruct subjects to inform site personnel when they are planning to receive medical care by another physician. At each visit, the investigator will ask the subject whether he/she has received medical care by another physician since the last visit or is planning to do so in the future. When the subject is going to receive medical care by another physician, the investigator, with the consent of the subject, will inform the other physician that the subject is participating in the clinical study.

9.6 Data Quality Assurance

This study will be organized, performed, and reported in compliance with the protocol, SOPs, working practice documents, and applicable regulations and guidelines. Site audits will be made periodically by the sponsor's or the CRO's qualified compliance auditing team, which is an independent function from the study team responsible for conduct of the study.

9.6.1 Data Collection

Data required by the protocol will be collected on the CRFs and entered into a validated data management system that is compliant with all regulatory requirements. As defined by ICH guidelines, the CRF is a printed, optical, or electronic document designed to record all of the protocol-required information to be reported to the sponsor on each study subject.

Data collection on the CRF must follow the instructions described in the CRF Completion Guidelines. The investigator has ultimate responsibility for the collection and reporting of all clinical data entered on the CRF. The investigator or designee as identified on Form FDA 1572 must sign the completed CRF to attest to its accuracy, authenticity, and completeness.

Completed, original CRFs are the sole property of Eisai and should not be made available in any form to third parties without written permission from Eisai, except for authorized representatives of Eisai or appropriate regulatory authorities.

9.6.2 Clinical Data Management

All software applications used in the collection of data will be properly validated following standard computer system validation that is compliant with all regulatory requirements. All data, both CRF and external data (eg, laboratory data), will be entered into a clinical system.

9.7 Statistical Methods

All statistical analyses will be performed by the sponsor or designee after the study is completed (based on the data cut off for the primary analysis) and the database is locked and released. The interim analyses will be performed by an independent statistical reporting team. Statistical analyses will be performed using SAS software or other validated statistical software as required. Details of the statistical analyses will be included in a separate statistical analysis plan (SAP).

9.7.1 Statistical and Analytical Plans

The statistical analyses of study data are described in this section. Further details of the analytical plan will be provided in the SAP, which will be finalized before database lock.

9.7.1.1 Study Endpoints

9.7.1.1.1 PRIMARY ENDPOINTS

- Objective response rate at Week 24 (ORR_{24W}) as assessed by the investigator according to RECIST 1.1 ([Appendix 8](#)). ORR_{24W} is defined as the proportion of subjects with best overall response (BOR) of complete response (CR) or partial response (PR) at the Week-24 (after randomization) time point or earlier. To be considered a BOR, all responses must be confirmed no less than 4 weeks after the initial assessment of response.
- Proportion of subjects with intolerable Grade 2 or any \geq Grade 3 TEAEs within 24 weeks after randomization (as of the Week-24 time point).

9.7.1.1.2 SECONDARY ENDPOINTS

- Progression-free survival (PFS), defined as the time from the date of randomization to the date of first documentation of disease progression or date of death or the date of data cutoff for the primary analysis, whichever occurs first. PFS censoring rules will be defined in the statistical analysis plan (SAP) and will follow FDA guidance.
- ORR as assessed by the investigator according to RECIST 1.1 at the end of treatment. ORR is defined as the proportion of subjects with BOR of CR or PR at the end of treatment. To be considered BOR, all responses must be confirmed no less than 4 weeks after the initial assessment of response.
- Overall safety profile and tolerability of lenvatinib in combination with everolimus.
- Proportion of subjects who discontinue treatment due to toxicity, defined as the proportion of subjects who discontinue study treatment due to TEAEs.

- Time to treatment failure due to toxicity, defined as the time from the date of randomization to the date that a subject discontinues study treatment due to TEAEs.
- Lenvatinib and everolimus exposure parameters and PK and PD drug-drug interactions.
- Overall survival (OS), measured from the date of randomization until date of death from any cause. In the absence of confirmation of death, subjects will be censored either at the date that the subject was last known to be alive or the date of data cutoff for the primary analysis, whichever comes earlier.
- Health-Related Quality of Life (HRQoL) will be assessed using the Functional Assessment of Cancer Therapy-Kidney Symptom Index-Disease Related Symptoms (FKSI-DRS), the European Organization for the Research and Treatment of Cancer (EORTC) QLQ-C30 and the European Quality of Life (EuroQol) EQ-5D-3L instruments.
- PFS2, defined as the time from randomization to the date of disease progression after next line of therapy or death from any cause or the date of data cutoff for the primary analysis, whichever occurs first. PFS2 censoring rules will be defined in the SAP.

9.7.1.1.3 EXPLORATORY ENDPOINTS

- Tumor response endpoints ORR_{24w}, ORR, and PFS based on IIR assessment. These endpoints will be defined in the same way as those based on the investigator assessments.
- Associations between blood biomarker and efficacy related endpoints.
- Development of exposure/biomarker/clinical endpoint models (whenever possible, using a mechanism-based approach) for both efficacy and safety data.

9.7.1.2 Definitions of Analysis Sets

Full Analysis Set will include all randomized subjects. This will be a secondary analysis set for efficacy endpoints, which will be analyzed according to the treatment randomized, regardless of the treatment actually received.

Per-Protocol Analysis Set 1 will include all randomized subjects minus the 32 subjects who had received ≥ 2 incorrect lenvatinib doses due to IxRS issues. This will be the primary analysis set for efficacy endpoints, which will be analyzed according to the treatment randomized.

Per-Protocol Analysis Set 2 will include all subjects who received at least 1 dose of study drug, had no major protocol deviations, and had both baseline and at least 1 post-baseline tumor assessment. Subjects for whom death occurred before the first post-baseline tumor assessment will also be included. The Per-Protocol Analysis Set 2 will be a secondary analysis set for efficacy endpoints. The 32 subjects who received ≥ 2 incorrect lenvatinib doses due to IxRS issues are considered as having experienced major protocol deviations and will be excluded from the Per-Protocol Analysis Set 2. (A 33rd subject received a single incorrect lenvatinib dose due to IxRS issues, but given the brief exposure of the incorrect [slightly higher] dose before detection and correction, and because there were no adverse

effects, this subject will be considered to have experienced a minor protocol deviation and will not be excluded from analysis sets.)

Safety Analysis Set will include all subjects who were randomized and received at least 1 dose of study drug. This will be the analysis set for all safety evaluations, which will be analyzed according to the treatment actually received.

Per-Protocol Safety Analysis Set will include all treated subjects in Per-Protocol Analysis Set 1. This will be the primary analysis set for the primary safety endpoint, which will be analyzed according to the treatment actually received.

Pharmacokinetic (PK) Analysis Set will include all subjects who received at least 1 dose of study drug with documented dosing history and have at least 1 evaluable lenvatinib plasma or everolimus whole blood concentration data.

Pharmacodynamic Analysis Set will include all subjects who received at least 1 dose of study drug with documented dosing history and have at least 1 evaluable pharmacodynamic data.

9.7.1.3 Subject Disposition

Subject disposition will be summarized for the Per-Protocol Analysis Set 1, Per-Protocol Analysis Set 2, and Full Analysis Set. All subjects who were screened for the study will be accounted for and reported in the study results. The reasons for screen failures will be described and documented by subject and summarized by total number of subjects with screen failures. If deemed relevant, the reasons for excluding subjects will be evaluated to determine if these reasons could help clarify the appropriate subject population for eventual drug use.

The number (percentage) of randomized and treated subjects will be summarized as well as subjects who completed the study/discontinued from the study and reasons for discontinuation by treatment arm. The number (percentage) of subjects who completed the study treatment/discontinued from the study treatment and reasons for discontinuation will also be summarized by treatment arm.

9.7.1.4 Demographic and Other Baseline Characteristics

Demographic and other baseline characteristics will be summarized for the Per-Protocol Analysis Set 1, Per-Protocol Analysis Set 2, and Full Analysis Set. For continuous demographic/baseline variables including age, weight, and height, results will be summarized and presented as N, mean, standard deviation, median, Q1, Q3, and minimum and maximum values. For categorical variables such as race/ethnicity, the number and percentage of subjects will be used.

9.7.1.5 Prior and Concomitant Therapy

Prior and concomitant therapy will be summarized for the Per-Protocol Analysis Set 1 and Full Analysis Set. All investigator terms for medications recorded on the CRF will be coded using the World Health Organization (WHO) Drug Dictionary. Prior medications will be defined as medications that were started prior to the first dose of study drug and were stopped prior to the first dose of study drug. Concomitant medications will be defined as medications that (i) started before the first dose of study drug and were continuing at the time of the first dose of study drug, or (ii) started on or after the date of the first dose of study drug up to 28 days following the last dose in randomization phase. Medications that cannot be determined

to be prior/concomitant/posttreatment due to missing or incomplete dates will be regarded as concomitant.

Prior medications will be summarized by anatomical class (Anatomical Therapeutic Chemical [ATC] Level 1), pharmacologic class (ATC Level 3), and World Health Organization (WHO, Geneva, Switzerland) generic drug name by frequency counts and percentages. The same summary will be provided for concomitant medications except thyroxine suppression therapy and hypertensive therapy. Concomitant thyroxine suppression therapy and hypertensive therapy will be summarized separately. In addition, there also will be a separate summary for the concomitant medications of P-glycoprotein inhibitors and/or inducers. Data listings will be provided for all prior and concomitant medications, for all concomitant thyroid suppression therapy, for all concomitant hypertensive therapy, and for all concomitant P-glycoprotein inhibitors and/or inducers.

9.7.1.6 Efficacy Analyses

9.7.1.6.1 PRIMARY EFFICACY ANALYSIS

Primary analysis of ORR_{24W} will be based on a non-inferiority test. There will be two interim analyses and the primary analysis. The two interim analyses will be performed using only Per-Protocol Analysis Set 1. The primary analysis will be performed using the Per-Protocol Analysis Set 1 as the primary analysis set and will also be performed using Per-Protocol Analysis Set 2 and the Full Analysis Set as secondary analysis sets. At each interim analysis and primary analysis, the point estimate of ORR_{24W} for each treatment group (18 mg and 14 mg) will be summarized with the corresponding 95% confidence interval (CI). The odds ratio of ORR_{24W} (14 mg vs 18 mg) along with the 90% CI will be calculated using the Cochran-Mantel-Haenszel (CMH) method stratified by MSKCC prognostic groups and prior PD-1/PD-L1 treatment. Non-inferiority in ORR_{24W} will be claimed if the O'Brien-Fleming efficacy boundary is crossed at either interim analysis or primary analysis based on the results from the Per-Protocol Analysis Set 1. If the 1-sided P -value is ≤ 0.005 at the first interim analysis, or ≤ 0.014 at the second interim analysis, or ≤ 0.045 at the primary analysis, non-inferiority in ORR_{24W} will be claimed. Futility will be claimed if the futility boundary is crossed. If the 1-sided P -value is ≥ 0.776 at the first interim analysis, or ≥ 0.207 at the second interim analysis, futility will be claimed. The treatment difference in ORR_{24W} for 14 mg vs 18 mg will also be estimated along with 90% CIs based on the asymptotic normal approximation.

At each interim analysis and at the primary analysis, if the noninferiority boundary of the primary efficacy endpoint is crossed, the analysis of the primary safety analysis will be performed for Per-Protocol Safety Analysis Set. The primary safety endpoint is the proportion of subjects with intolerable Grade 2 or any \geq Grade 3 TEAEs within 24 weeks after randomization (as of the Week-24 time point). Frequency (number and percentage) will be summarized for intolerable Grade 2 or any \geq Grade 3 TEAEs within 24 weeks after randomization by treatment. The proportions will be tested using the CMH test (2-sided $\alpha=0.05$), stratified by MSKCC prognostic groups and prior PD-1/PD-L1 treatment. The proportions of the primary safety endpoint will also be summarized for Safety Analysis Set for descriptive purpose.

To explore homogeneity of treatment effect across centers/regions, sensitivity analyses will be conducted to adjust center/region effect for the primary endpoints of ORR_{24W} and proportion of subjects with intolerable Grade 2 and any \geq Grade 3 TEAEs within 24 weeks after randomization using logistic regression models, including center/region as a covariate.

Determination of whether 14 mg lenvatinib can be used as an alternative dosing strategy will be based on clinical judgment by the sponsor in consultation with the independent DMC (as specified in the DMC charter) by assessing risks and benefits according to the totality of the safety and efficacy data.

9.7.1.6.2 SECONDARY EFFICACY ANALYSES

All secondary efficacy endpoints will be summarized descriptively for the Per-Protocol Analysis Set 1, Per-Protocol Analysis Set 2, and Full Analysis Set. The median PFS and PFS2 will be calculated using the KM product-limit estimates for each treatment group and presented with 2-sided 95% CIs. The KM estimate of PFS will also be plotted over time for each treatment group.

Point estimate of ORR and 95% CI will be summarized for each treatment arm. Odds ratio with 90% CI will be estimated using the CMH method stratified by MSKCC prognostic groups and prior PD-1/PD-L1 treatment.

The median survival time and the survival rates at 12, 18, and 24 months will be calculated using KM product-limit estimates for each treatment group and presented with 2-sided 95% CIs. The KM estimates of OS will be plotted over time.

For HRQoL analyses, summary statistics of the scores for the derived functional/symptom scales according to the scoring manual and global health status scores will be summarized by treatment arm at each time point. A separate pre-specified HRQoL analysis following FDA and EMEA patient-reported outcome (PRO) guidelines will be performed and detailed in a separate SAP and HRQoL report. Scoring of EQ-5D-3L and derivation of utility for health economic analysis will also be accomplished in a separate analysis and described in a separate HRQoL report.

9.7.1.6.3 EXPLORATORY EFFICACY ANALYSES

All exploratory endpoints will be summarized descriptively. Exploratory efficacy response endpoints ORR_{24W}, ORR, and PFS based on IIR assessment will be summarized using the same statistical methods as those used for the same response parameters based on the investigator assessments.

9.7.1.6.4 HANDLING OF MISSING DATA FOR EFFICACY ANALYSES

For efficacy endpoints related to ORR which summarizes the percentage of responders, missing responses will not be imputed and subjects with missing response will be considered as non-responders. For incomplete dates involving efficacy data, a conservative imputation rule will be used for calculation if needed. Details of handling missing data and imputation rules will be specified in SAP and further in the study analysis dataset specifications.

HRQoL analysis will follow FDA and EMEA PRO guidelines. Handling of missing values for HRQoL analyses will be detailed in a separate SAP and HRQoL report.

9.7.1.7 Pharmacokinetic, Pharmacodynamic, and Other Biomarker Analyses

Lenvatinib and everolimus concentrations will be summarized by use of descriptive statistics and plotted as appropriate for each treatment group.

Concentrations of lenvatinib in plasma and everolimus in whole blood will be pooled with existing data from other completed studies and analyzed using a population PK approach to estimate population PK parameters for each drug. The analyses will be detailed in a separate analysis plan.

9.7.1.7.1 PHARMACOKINETIC/PHARMACODYNAMIC ANALYSES

Lenvatinib and everolimus exposure parameters (AUC or concentration at the time of the event or cumulative AUC, as appropriate) derived from the population PK analysis will be related to biomarker, safety, and efficacy data using a model-based approach. For some PK/PD analyses, data from this study will be pooled with data from the Phase 2 Study E7080-G000-205 (Study 205).

For the exposure-response relationship for biomarkers (e.g., VEGF, Ang-2), data will be analyzed using a model-based approach with indirect PK/PD models.

For efficacy, a tumor growth inhibition model based on longitudinal tumor size measurements of target lesions will be included. Study drug exposure for lenvatinib and everolimus and/or measured biomarkers (e.g., VEGF, Ang-2) will be investigated as predictors and/or correlations with tumor burden changes in the tumor growth inhibition model, whenever possible using a mechanism-based approach.

Other analyses will include logistic regression analysis for ORR_{24w}, KM plots of PFS data, and Cox-regression analysis. For the Cox-regression analysis of PFS, adjustment will be made for subject's baseline characteristics or tumor-related features. In addition to lenvatinib and everolimus exposure, changes in biomarker concentrations and/or tumor burden will be related to PFS, whenever possible using a mechanism-based approach.

For the exposure-response relationship of safety, the model-based analysis will include the following AEs: hypertension (systolic and diastolic BP), triglyceridemia (and cholesterolemia), glycemia, proteinuria, weight loss, fatigue, nausea, vomiting and diarrhea. For hypertension, triglyceridemia (and cholesterolemia) and glycemia, data will be analyzed using an indirect-response model. For proteinuria, urine dipstick and/or 24-hour urine data will be analyzed using a longitudinal categorical logistic regression analysis with Markov element. For weight loss, fatigue, nausea, vomiting, and diarrhea, data will be analyzed using a longitudinal categorical logistic regression analysis. For time to treatment discontinuation due to an AE and time to first dose reduction, KM plots stratified by lenvatinib exposure will be prepared.

Population PK and PK/PD analyses will be detailed in a separate analysis plan.

9.7.1.7.2 BIOMARKER ANALYSES

The effect of lenvatinib and everolimus combination treatment on exploratory biomarkers will be summarized by treatment group. Associations between clinical outcomes and baseline biomarker levels, and/or change in levels from baseline will be explored. The analysis will be detailed in the biomarker analysis plan (BAP) and reported separately.

For exploratory endpoints, Pharmacokinetic, Pharmacodynamic and Other Biomarker endpoints, their respective analysis plans will specify if the analyses will and will not include the 32 subjects who received ≥ 2 incorrect lenvatinib doses due to IxRS issues.

9.7.1.8 Safety Analyses

All safety analyses will be performed on the Per-Protocol Safety Analysis Set and Safety Analysis Set. All safety analyses will be summarized separately by treatment group. The incidence of TEAEs, intolerable Grade 2 TEAEs that lead to dose interruption, dose reduction, or drug discontinuation, \geq Grade 3 TEAEs, and SAEs will be summarized; rates will be summarized using descriptive statistics.

Time to treatment discontinuation due to an AE, number of dose reductions, and time to first dose reduction will be summarized. The proportion of subjects who discontinue treatment due to toxicity will be summarized by frequency counts and percentages. Median, upper, and lower quintiles of time to treatment discontinuation due to toxicity will be summarized for subjects who discontinue study treatment due to TEAEs.

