To explore homogeneity of treatment effect across centers/regions, sensitivity analyses will be conducted to adjust center/region effect for the primary endpoints of ORR_{24W} and proportion of subjects with intolerable Grade 2 and any \geq Grade 3 TEAEs within 24 weeks after randomization using logistic regression models, including center/region as a covariate.

Determination of whether 14 mg lenvatinib can be used as an alternative dosing strategy will be based on clinical judgment by the Sponsor in consultation with the independent Data Monitoring Committee (DMC) (as specified in the DMC charter) by assessing risks and benefits according to the totality of the safety and efficacy data.

Analysis of Secondary Endpoints:

All secondary efficacy endpoints will be summarized descriptively for the Per-Protocol Analysis Set 1, Per-Protocol Analysis Set 2, and Full Analysis Set. The median PFS and PFS2 will be calculated using the Kaplan-Meier (KM) product-limit estimates for each treatment group and presented with 2-sided 95% CIs. The KM estimate of PFS will also be plotted over time for each treatment group.

Point estimate of ORR and 95% CI will be summarized for each treatment arm. Odds ratio with 90% CI will be estimated using the CMH method stratified by MSKCC prognostic groups and prior PD-1/PD-L1 treatment.

The median survival time and the survival rates at 12, 18, and 24 months will be calculated using KM product-limit estimates for each treatment group and presented with 2-sided 95% CIs. The KM estimates of OS will be plotted over time.

All safety analyses will be performed on the Per-Protocol Safety Analysis Set and the Safety Analysis Set and summarized by treatment group.

The proportion of subjects who discontinue treatment due to toxicity will be summarized by frequency counts and percentages. Median, upper, and lower quintiles of time-to-treatment failure due to toxicity will be summarized for subjects who discontinue study treatment due to TEAEs.

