Median time to first dose reduction with 95% CI will also be estimated based on Kaplan-Meier method for all the treated subjects. Subjects who did not have dose reductions during treatment period will be censored at the date of last dose.

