5.6.3.6 TEAEs Leading to Treatment Discontinuation

The proportion of subjects who discontinued treatment due to toxicity and time to treatment discontinuation due to toxicity will be summarized descriptively.

The TEAEs leading to treatment discontinuation (discontinuation of both study drugs in each treatment arm) will be summarized by SOC and PT for those subjects indicated as having discontinued study treatment due to an adverse event on the CRF treatment disposition page.

The TEAEs leading to study drug discontinuation for each individual drug will also be summarized.

A listing of AEs leading to treatment discontinuation or any study drug discontinuation will be provided.

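### The protocol summarizes time to treatment failure due to toxicity only among subjects who failed, the SAP is vaguer and points elsewhere, and neither gives a censoring or competing-event rule

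*Protocol*

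**What the plan says.** - **Endpoint.** Protocol 9.7.1.1.2 defines time to treatment failure due to toxicity as "the time from the date of randomization to the date that a subject discontinues study treatment due to TEAEs". SAP 5.1.2 has the same definition. Neither says what happens to a subject who does not have the event.
- **Protocol analysis.** Section 9.7.1.8 says the median and the upper and lower quintiles of the time to a toxicity stop "will be summarized for subjects who discontinue study treatment due to TEAEs". The synopsis has the same restriction and uses the endpoint's own name: "time-to-treatment failure due to toxicity will be summarized for subjects who discontinue study treatment due to TEAEs".
- **SAP analysis.** Section 5.6.3.6 says that "time to treatment discontinuation due to toxicity will be summarized descriptively". It does not repeat the restriction and does not name an estimator, a population or a censoring rule. The opening paragraph of SAP section 5 says that, in general, variables timed from randomization to an event are described by Kaplan-Meier.
- **Frequency.** The proportion stopping for toxicity is a separate secondary endpoint in Protocol 9.7.1.1.2: "Proportion of subjects who discontinue treatment due to toxicity, defined as the proportion of subjects who discontinue study treatment due to TEAEs". Protocol 9.7.1.8 covers its analysis: "The proportion of subjects who discontinue treatment due to toxicity will be summarized by frequency counts and percentages". Safety summaries are by treatment group.
- **Nearest comparison.** For time to first dose reduction, SAP 5.6.2.3 gives a summary among subjects who had a reduction and adds: "Median time to first dose reduction with 95% CI will also be estimated based on Kaplan-Meier method for all the treated subjects". Subjects without a reduction are censored at their last dose.

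**The concern.** Better tolerability of the 14-mg start is half of the primary objective, and the dosing decision rests on the totality of safety and efficacy data (Protocol 9.7.1.6.1). This endpoint is there to show when toxicity ends treatment in each arm.

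A median taken only over subjects who had the event cannot do that well. It discards the time that all other subjects spent on treatment without a toxicity stop. What remains depends mainly on how long subjects stay under observation before any exit or the data cutoff, and only weakly on the toxicity rate. Two arms with very different toxicity rates can show nearly the same median, and in a trial of this size the order can reverse by chance. A reader of the report could then conclude that the lower start does not delay toxicity stops when in fact it does.

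**Working it through.** The plan gives no event count, power or expected value for this endpoint, so there is no figure of its own to reproduce. The check is how a failures-only median responds when the toxicity hazard is roughly halved.

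**Model.** Constant hazards: *h* for a toxicity stop, *g* for any other exit, follow-up *T* months. Let *L* = *h* + *g* and *F* = 1 − exp(−*LT*).

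- Proportion stopping for toxicity = (*h*/*L*) × *F*
- Median time among those who stopped for toxicity = −ln(1 − *F*/2)/*L*

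The median depends on *h* only through the total *L*. If other exits dominate, changing *h* hardly moves it.

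**Set A (all inputs assumed):** *g* = 0.08 per month, *T* = 12.

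| | *h* = 0.03 | *h* = 0.015 |
|---|---|---|
| *L* | 0.110 | 0.095 |
| *F* | 1 − exp(−1.32) = 0.733 | 1 − exp(−1.14) = 0.680 |
| Stop for toxicity | (0.03/0.110) × 0.733 = 20.0% | (0.015/0.095) × 0.680 = 10.7% |
| Failures-only median | −ln(1 − 0.366)/0.110 = 4.15 months | −ln(1 − 0.340)/0.095 = 4.38 months |

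A simulation of 200,000 per arm gave 4.19 and 4.42 months. Halving the hazard moves the median by about a quarter of a month.

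**Set B.** One arm is set at 23.5% stopping for toxicity, the Study 205 combination-arm rate for discontinuation due to adverse events (Protocol 7.1). The other is assumed to have half that, 11.75%. The median time to other exits is assumed to be 12 months (*g* = ln 2/12 = 0.0578), with *T* = 24. The hazards that give those proportions are 0.0220 and 0.0099 per month, a ratio of 0.45.

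| | 23.5% arm | 11.75% arm |
|---|---|---|
| Failures-only median | 6.97 months | 7.58 months |
| Cumulative incidence at 6 months, all subjects | 10.5% | 4.9% |

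**Range.** With the median time to other exits at 8, 12 or 18 months and follow-up of 12 or 24 months, the failures-only medians differ by 0.26 to 0.61 months. The hazard ratio stays at 0.44 to 0.46 throughout.

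**At the trial's size.** With 153 per arm (the planned Per-Protocol Analysis Set 1), 5,000 simulated trials under Set B gave the better arm an equal or earlier failures-only median in 41% of trials. Under Set A the figure was 44%.

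**The case against.** The strongest reply is that the SAP already provides a sound analysis. Section 5.6.3.6 drops the protocol's restriction, the endpoint runs from randomization, and SAP section 5 assigns Kaplan-Meier to such variables. Time to first dose reduction runs from first dose, so it falls outside that general definition and needed its own Kaplan-Meier sentence. The contrast between the two is therefore weaker than it looks. Protocol 9.7.1.8 also has an unrestricted sentence saying that time to discontinuation due to an AE will be summarized.

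Much of this stands. A reader might infer that the failures-only summary is the only analysis the two documents allow, and the SAP text does not support that. It does not resolve the problem, though. The general rule is a default, and it carries no censoring or competing-event rule for progression, death or other exits. SAP section 7 declares no change from the planned analyses, so the protocol's restriction is not withdrawn. The Kaplan-Meier plots of time to discontinuation in Protocol 9.7.1.7.1 are split by lenvatinib exposure, not by randomized arm.

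A reader might also infer that the plan hides how often toxicity stops treatment. It does not. The proportion is its own secondary endpoint, reported by arm alongside the time summary. In Set A the contrast of 20.0% and 10.7% would be in plain view.

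It is also fair that the size of the effect rests on assumed hazards, and that the endpoint is descriptive. The formal tolerability test is the 24-week primary safety endpoint, which is unaffected.

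**Conclusion.** The point holds for timing. The protocol specifies a failures-only median and quintiles, the SAP neither confirms nor replaces them, and no rule covers subjects who leave treatment for other reasons or are still on it at cutoff.

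The specified statistic is nearly blind to what the endpoint should measure. In the scenarios checked, a toxicity hazard about half as large shifts it by roughly a quarter to 0.6 of a month, and at 153 per arm it fails to favor the better arm in about 41% to 44% of simulated trials. Those sizes depend on constant hazards and on assumed exit rates and follow-up. Only the 23.5% and the 153 per arm come from the documents. The weak response to the toxicity hazard held across the whole range tried.

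This is a correction worth making to a secondary, descriptive endpoint. It does not threaten the primary analyses.

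**What to change.** In SAP 5.6.3.6, state one analysis by arm:

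- **Population and time.** All treated subjects, from randomization to discontinuation due to TEAEs.
- **Method.** Cumulative incidence, with other discontinuations and death as competing events and subjects still on treatment censored at the data cutoff. Kaplan-Meier with an explicit censoring rule would also be acceptable.
- **Output.** 24-week estimates by arm with 95% CIs.
- **Failures-only quantiles.** Keep them only as a supplement, labelled as conditional on having stopped for toxicity.

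Record the departure from Protocol 9.7.1.8 and the synopsis in SAP section 7, which now reads as not applicable.

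The cost is one SAP paragraph, one entry in section 7 and the matching output. The discontinuation reason and last-dose date are already collected (Protocol 9.3.3). No test, alpha or sample size changes.
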